Following the infusion, the participants will be observed for one hour before being allowed to return home. The risk management of the infusion are described in item 5.3. In the next 2 to 3 days, the participants will be referred to have a MRI at Medscan Bangaroo. All Nano MRL scans will be double assessed by two experienced readers (one at I-Med Radiology and the other at The Wesley Hospital) and then by an experienced reader of Radboud University Nijmegen, the Netherlands.

The assessment of Nano MRL and 68Ga-PSMA PET scans represents a crucial endpoint in this study. Consequently, before the start of the trial we will define imaging standards and provide an intensive training of image interpretation. In order to ensure a homogeneous high quality of image assessment according to the requirements of MAGNIFI Trial, extensive effort will be made for training, including a 10 days training at the Radboud University Nijmegen the Netherlands. To assure the quality of this training, each investigator judging the images in the MAGNIFI Trial will have to pass a certification.

3. *Radical prostatectomy with pelvic lymph node dissection*

Patients will undergo radical prostatectomy and extended pelvic lymph node dissection, as clinically indicated within 7-10 days following Combidex nano-MRL imaging, with all dissected lymph node packets being dissected and labelled. Suspicious lymph nodes detected on nano-MRL or PSMA will be specifically targeted for resection during lymph node dissection.

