This will be done at the The Kinghorn Cancer Centre (a facility of the St Vincent's Hospital) with a full anaphylaxis and resuscitation kit at the bedside, as well as an anaesthetist who is present in the hospital being on standby for emergencies. The intensive care staff will also be advised of the trial and will be notified in advance each day that patients are having an infusion, with a team member on standby by phone in the case of emergency. These extra-ordinary precautions will hopefully ensure that any adverse event during infusion is rapidly dealt with and controlled with minimal risk to patients. Should adverse reactions be noted at anytime throughout the procedure, the infusion will be stopped immediately and the St Vincent's Hospital IV Contrast Allergy Protocol will be referred to.

Upon the completion of Combix infusion, each patient will be required to remain at St. Vincent's Hospital for at least one hour.

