3. Prepare the correct dose of Iron-Dextran Nanoparticles “(NANO contrast fluid “Combidex”) based on the dose table in this protocol and dissolve in 100ml 0.9% Sodium Chloride.
4. Review the dose and fluid calculations with a second practitioner.
5. Make sure the name and date of birth is specified on the NANO contrast fluid (Combidex).

Administration:

1. Put in the 18G intravenous cannula
2. Connect the 100ml 0.9% Sodium Chloride and start slow infusion
3. Call [name] (radiologist) to administer the NANO contrast fluid (Combidex)
4. The radiologist will change the 100ml 0.9% Sodium Chloride for the NANO contrast fluid (Combidex) and will specify date and time start infusion
5. The NANO contrast fluid (Combidex) will be administered in at least 30 minutes
6. At the time the NANO contrast fluid (Combidex) is completed, infusion will be changed to 0.9% Sodium Chloride will a slow rate.
7. Remove the intravenous cannula
8. The patient must remain at the health centre for at least 60 minutes after the end of infusion

Side effects:

Like every medical product, the NANO contrast fluid could have side effects. Side effects include headache, dizziness, light-headedness, nausea, an itchy skin. Normally, these side effects will resolve after a short period.

Allergic reaction:

Anaphylaxis is a severe, potentially fatal allergic reaction. It is characteristically unexpected and rapid in onset. If a patient has an anaphylaxis, the anaphylaxis protocol of St Vincent’s Hospital should be followed: appendix IV Contrast Allergy Protocol.

Should adverse reactions be noted at any time throughout the infusion:

1. **Stop the infusion immediately**
2. **Contact [name] (radiologist)**
3. **Refer to anaphylaxis protocol of St Vincent’s Hospital IV Contrast Allergy Protocol.**

IV CONTRAST ALLERGY PROTOCOL

5. Treatment of contrast reactions

Mild

Nausea / Vomiting

Supportive measures (antiemetics if prolonged vomiting)

Urticaria (mild)

Supportive measures

Urticaria (protracted)

Antihistamine (oral or intramuscular depending on severity)

Moderate

Marked Urticaria

- Antihistamines
- Consider use of Adrenaline 1:1000
 - In adults 0.1-0.25ml (0.1-0.25mg) intramuscularly – repeat as necessary
 - In children 0.01 mg/kg intramuscularly up to 0.3mg maximum dose

Bronchospasm

1. Oxygen by mask (6-10 l/min)
2. β -2-agonist (e.g. Salbutamol or Terbutaline) metered dose inhaler (2-3 deep inhalations).
In more severe cases, give Salbutamol or Terbutaline by nebuliser.

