3. Consider Adrenaline
 - Normal blood pressure*
In adults: 1:1,000, 0.1-0.25 ml (0.1-0.25 mg) intramuscularly
[use smaller dose in patients with coronary artery disease or elderly patients]
In paediatric patients: 0.01 mg/kg up to 0.3 mg max intramuscularly
 - Decreased blood pressure*
In adults: 1:1,000, 0.5 ml (0.5 mg) intramuscularly
In paediatric patients: 0.01 mg/kg intramuscularly

Hypotension

- Isolated hypotension
 1. Elevate patient's legs
 2. Oxygen by mask (6-10 l/min)
 3. Intravenous fluid: rapidly, normal saline or lactated Ringer's solution
 4. If unresponsive: adrenaline: 1:1,000 , 0.5 ml (0.5 mg) intramuscularly, repeat as needed
- Vaso-vagal reaction (hypotension and bradycardia)
 1. Elevate patient's legs
 2. Oxygen by mask (6-10 l/min)
 3. Atropine
 - In adults 0.6-1.0 mg intravenously, repeat if necessary after 3-5 min, to 3 mg total (0.04 mg/kg).

- In paediatric patients give 0.02 mg/kg intravenously (max. 0.6 mg per dose) repeat if necessary to 2 mg total.
- 4. Intravenous fluids: rapid infusion of normal saline or Hartmann's solution 20 ml/kg, repeat as necessary.

Severe

Generalized anaphylactoid reaction

1. Stop contrast injection
2. Call for resuscitation team
3. Suction and maintain airway as needed
4. Oxygen by mask (6 – 10 l/min)
5. Intramuscular adrenaline, intramuscularly into the lateral thigh

In adults (and in children >25 kgs), Adrenaline 1:1,000

| | |
|---------|--------------------|
| < 50 kg | give 0.25 – 0.5 mL |
| > 50 kg | give 0.5 mL |

In children, Adrenaline 1:1,000

| | | |
|---------|-------|--------------|
| 1 year | 10 kg | give 0.1 mL |
| 3 years | 15 kg | give 0.15 mL |
| 5 years | 20 kg | give 0.2 mL |
| 8 years | 25 kg | give 0.25 mL |

- If necessary, repeat intramuscular dose every 5 minutes.
 - Large doses of adrenaline may be needed, up to a maximum of 5 mL (5 mg).
 - If the patient remains shocked after two intramuscular doses, consider an adrenaline infusion to restore blood pressure. (See notes 3,4).
6. Intravenous fluids (e.g. normal saline or Hartmann's solution 20mL/kg). Continue as necessary
 7. Ventilate patient if severe respiratory and circulatory collapse
 8. Additional measures:

| | |
|----------------------|---|
| Bronchodilators | For bronchospasm, give salbutamol or terbutaline by nebuliser, or aerosol with spacer device. |
| Corticosteroids | Hydrocortisone 2-6mg/kg or Dexamethasone 0.1-0.4 mg/kg intravenously |

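### Appendix C takes the cannula out before the post-infusion observation hour, although its allergy protocol treats three reaction types partly by the intravenous route

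*Protocol*

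**What the plan says.** Appendix C of the protocol (version 1.0, September 2015) sets out the Combidex infusion as eight numbered administration steps. The last three matter here:

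- Step 6, once the contrast has run in: "infusion will be changed to 0.9% Sodium Chloride will a slow rate". No duration is given.
- Step 7: "Remove the intravenous cannula". No time or condition is given.
- Step 8: "The patient must remain at the health centre for at least 60 minutes after the end of infusion".

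The body of the protocol repeats the hour. Section 5.2 (Imaging) makes it a period of observation: "Following the infusion, the participants will be observed for one hour before being allowed to return home". Section 5.3 also requires a stay of at least an hour at the hospital ("Upon the completion of Combix infusion, each patient will be required to remain at" St Vincent's).

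Section 5.3 places the infusion in a hospital facility "with a full anaphylaxis and resuscitation kit at the bedside", with an anaesthetist on standby in the hospital and an intensive care team member on call by phone. It sends reactions to the hospital's allergy protocol, which is reproduced in Appendix C: "Should adverse reactions be noted at anytime throughout the procedure, the infusion will be stopped immediately". That trigger covers the whole procedure, so it is not a gap.

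**The concern.** The observation hour is there to catch reactions to an agent for which section 5.3 itself acknowledges hypersensitivity, anaphylaxis and cardiac risk. Staff normally work through a numbered list in order. Followed that way, Appendix C removes the cannula before the stay is complete, while the emergency plan in the same appendix relies partly on the intravenous route.

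If a reaction began after removal, intravenous fluid and intravenous drugs would wait for a new cannula, possibly in a man whose blood pressure had already fallen. What is at stake is an avoidable delay in part of the emergency treatment. No estimate, test or sample size in the trial is touched.

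**Working it through.** The plan gives no statistical figure on this point, so the check sets the texts side by side and counts.

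**1. Order of steps.** Cannula removal is step 7 and the 60-minute stay is step 8. Sections 5.2 and 5.3 and all of Appendix C contain no requirement to keep venous access during the hour.

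**2. Possible time without access.** Take the end of infusion in step 8 to mean the end of the contrast, as section 5.3 does. Let *t* be the minutes from then until step 7, which the protocol does not state. Within the minimum stay, the time without access is 60 − *t*:

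| *t* (min) | Without access (min) |
|---|---|
| 0 | 60 |
| 30 | 30 |
| 60 | 0 |

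The slow saline of step 6 makes *t* greater than zero, but by an unstated amount.

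**3. Reaction types that use the intravenous route in adults.** The allergy protocol lists eight types: nausea or vomiting, mild urticaria, protracted urticaria, marked urticaria, bronchospasm, isolated hypotension, vaso-vagal reaction and generalized anaphylactoid reaction. The first five state no intravenous treatment. The other three do:

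| Reaction | First intravenous step | Numbered steps before it | Intramuscular drug listed |
|---|---|---|---|
| Isolated hypotension | Step 3, fluid ("Intravenous fluid: rapidly, normal saline or lactated" Ringer's) | 2 (leg elevation, oxygen) | Adrenaline, step 4, if unresponsive |
| Vaso-vagal reaction | Step 3, atropine; fluid at step 4 | 2 (leg elevation, oxygen) | None |
| Generalized anaphylactoid | Step 6, fluid | 5 | Adrenaline, step 5 |

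The count is 3 of 8. Isolated hypotension and vaso-vagal reaction share one main heading; counting by heading gives 2 of 7. In the anaphylactoid row, step 1 (stopping the contrast) no longer applies once the infusion is over, so 5 − 1 = 4 steps are relevant in the observation hour. That entry also lists intravenous corticosteroid at step 8 and an adrenaline infusion to be considered if shock persists after two intramuscular doses. The notes add intravenous glucagon for cases resistant to adrenaline.

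**4. Which entry depends most on access.** The vaso-vagal reaction: its only drug and its fluid are both intravenous.

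**5. Exposure.** The order applies to 120 planned first infusions, plus any repeat infusion under the re-imaging rule in section 5.2. The documents give no rate of reactions that start after the infusion and need intravenous treatment, so no number of affected men can be derived.

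**The case against.** The strongest reply is that nothing here is stated wrongly. Step 8 says when the man may leave, not when the line comes out. Step 7 has no time, and the slow saline of step 6 keeps the line open for some period just after dosing, when a rapid reaction is most likely. In a generalized anaphylactoid reaction, adrenaline is intramuscular and comes before any intravenous step. A kit is at the bedside and trained help is on call. The safety record in section 5.3 shows no late reaction needing intravenous treatment: the one reported death occurred during a rapid infusion, and the two events among more than 200 patients at the Dutch centre were dizziness, relieved by pausing the infusion, and a mild cellulitis.

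Most of this stands, and it keeps the point small. The list permits a gap rather than ordering one, and the realistic consequence is a delay for re-cannulation with help nearby.

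It does not close the gap. Steps 7 and 8 can be followed exactly as printed with no access for nearly the whole hour. A bedside kit is not venous access. The vaso-vagal entry offers no non-intravenous drug, and isolated hypotension reaches intramuscular adrenaline only after intravenous fluid.

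**Conclusion.** The concern holds, as a minor patient-safety point. The printed order allows the cannula to be removed before an observation period intended to catch reactions, and no other text keeps access open. The possible gap is 0 to about 60 minutes per infusion, and three of the eight listed reaction types use the intravenous route in adults.

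This rests on two readings: that staff follow the steps in their numbered order, and that the hour runs from the end of the contrast. No claim is made about how often the gap would matter, because the documents give no basis for one.

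**What to change.** Swap the last two steps of the administration list in Appendix C:

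- *Step 7:* leave the cannula in place while the man completes the observation period of at least 60 minutes.
- *Step 8:* take the cannula out when that period is over, just before discharge.

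Two optional additions would tidy the text. State how the line is kept usable during the hour (slow saline continued, or capped and flushed), since step 6 gives no duration. Extend the Appendix C heading on adverse reactions, which mentions only the infusion, to cover the observation hour as well; this only aligns it with section 5.3.

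The cost is two lines in an appendix. No visit or staff time is added, because the man already stays and the cannula is already in. The downside is up to about one more hour of cannula time. For scale, section 5.3 reports one mild injection-site cellulitis among more than 200 patients: 1/200 = 0.5%, so under 0.5%. It does not say how long that cannula had been in.

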Appendix D: Repeat Combix (ferumoxtran-10) correspondence from [name], 15th March 2018

Radboudumc

Radboud university medical center
Radiology and Nuclear Medicine
Location Radiology

[name]
The Netherlands
Internal postal code 766
[name]
Radboudumc Main entrance, route 767
T [contact]
F [contact]

Head of Department
[name]
www.radboudumc.nl/rng

Dutch Chamber of Commerce
trade register 41055629/4

766

To whom it may concern,

| | | |
|----------------|---------------|--------|
| Date | Our reference | Page |
| March 15, 2018 | | 1 of 1 |
| Your reference | Contact | |

L.S.,

With this letter I want to make the statement,
that I have given many multiple injections with ferumoxtran-10 to the same patients.
Thus far this has caused no problems whatsoever.
Thus, if needed, the patients can have without additional risk a second or even more injections.

Kind regards,

[name],

Professor of Radiology,
Chairman Prostate MR-Reference/Expertise Center

[contact]
P [contact], or [contact]
CV: <[name]>

Radboud University Medical Center

Department of Radiology and Nuclear Medicine (767)
[name], The Netherlands
[name]
www.radboudumc.nl

908860

